# For patients not on HD or Peritoneal Dialysis

• Estimated glomerular filtration rate below 59 mL/min per 1.73 m^2.

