## 6. Research Plan

The current study proposes to recruit up to 50 participants in order to have 40 completers. Eligible CKD patients with MDD will be randomly assigned to 12 weeks of open label, flexible dose treatment with either Bupropion SR (N=20) or Fluoxetine (N=20). Patients will be recruited from the UAMS dialysis center or other local dialysis centers via flyers, referral by their treating physician and/or newspaper ads. Written consent will be obtained before any study procedures. Subjects are randomly assigned to open label treatment with one of the following:

• Bupropion group:

Version #: 17, IRB #203076

PI: [name]

 For patient not on hemodialysis or peritoneal, oral administration of bupropion SR tablet at a dose of 150 mg daily. Bupropion SR doses will be adjusted upward or downward based on tolerability and response.

- For patient on hemodialysis or peritoneal dialysis, oral administration of bupropion SR tablet at a dose of 150 mg on the 1st and the 3rd dialysis day of each week. Bupropion SR doses will be adjusted upward or downward based on tolerability and response.
- Fluoxetine group: Oral administration of fluoxetine tablet will be started at a dose of 10 mg/day for the
  first week and then increased, as tolerated to 20 mg/day for weeks 2–4. After this, doses will be
  adjusted based on clinical response and side effects up to a maximum dose of 60 mg/daily by week
  10.

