Participants will receive the study medication during the baseline assessment and instructed to begin the medication on day 1 (1st dialysis day) of week 1 of the study. For patient on hemodialysis or peritoneal dialysis, generic bupropion SR will be dosed at 150 mg on the 1st and the 3rd dialysis day of each week with doses adjusted upward or downward based on tolerability. The initial dose of bupropion-SR is based on the findings of Worrall et al [80], who measured plasma bupropion levels in a pharmacokinetic study of bupropion in HD patients. For patient not on hemodialysis or peritoneal dialysis, generic bupropion SR tablet will be dosed at 150 mg daily. Bupropion SR doses will be adjusted upward or downward based on tolerability and response. Fluoxetine will be started at 10 mg/day for the first week and then increased, as tolerated to 20 mg/day for weeks 2–4. After this, doses will be adjusted based on clinical response and side effects up to a maximum dose of 60 mg/daily by week 10 [62]. At the week 12 visit, the participants will stop the medication or may undergo a 1-2 week taper (depending on maintenance dose) if they are on a dose of fluoxetine that is higher than 20 mg.

Subjects will be seen during weeks 1, 2, 3, 4, 6, 8, 10, and 12 in face-to-face meetings by a rater blind to study medication and a study physician for Ham-D ratings, CGI, medication accountability, and measurement of adverse events. On weeks 5, 7, 9 and 11, subjects will come in to return the previous week's pill bottles and pick up the current week's medication. Table 1 shows study procedures. Medication will be prepared by UAMS Research Pharmacy, labeled with the directions for use and contact information, and given to participants by study staff on a weekly basis. Compliance will be monitored using the MAFV at each scheduled encounter and by analysis of antidepressant blood levels. Results of a second EKG done during week 4 will be reviewed to ensure QTc interval is less than 500 msec.

In order to control for the potential confound of chronic pain we will characterize it with the physical and psychological pain scale and with two objective measures, i.e. the pressure pain threshold and the Quantitative Sensory Test (QST).

Version #: 17, IRB #203076

PI: [name]

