#### **Biochemical Measurements:**

Plasma for inflammatory markers, TRP, and TRP metabolites will be obtained at mid-week prior to dialysis on weeks 1, 4, and 12. Blood fluoxetine and hydroxyl-bupropion levels will be obtained at weeks 4, and 12. When possible, samples will be taken from pre-filtered blood at the dialysis site and sent to a research laboratory core at UAMS and/or UT San Antonio for analysis. Twenty ml of venous blood will be collected as described in Table 1. Blood for free- and total-TRP and large neutral amino acids (LNAA) will be assayed by high performance liquid chromatography with coulometric detection (HPLC) [105] and expressed in µM. Plasma KYN concentrations will be determined by HPLC [106]. Quinolinic acid will be quantified by electron capture negative chemical ionization gas chromatography/mass spectrometry with [180] QUIN as internal standard [107]. Determinations of plasma concentrations of CRP, IL-1β, IL-6, and TNF-α will be performed by ELISA with the use of Quantikine High Sensitivity kits (intra-assay coefficient of variation for these cytokines 2.0 to 8.6%; interassay coefficient of variation 3.9 to 7.0%; R&D Systems, Minneapolis, MN) following established guidelines [108]. Bupropion and its active metabolites hydroxybupropion and fluoxetine and norfluoxetine will be analyzed using HPLC and mass spectrometry (MS) [109] [110].

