General Methods: Given that a primary goal of the current study is to obtain data to justify and support the feasibility of a future definitive trial, a variety of data necessary for this, including data on tolerability and safety (see below), will be obtained. For example, subject disposition will be summarized with a table indicating the number of subjects screened, the number of screen failures by reason, the number enrolled, the number who dropped out (by reason), and the number completing the study. Random double-blind assignment of patients to fluoxetine or bupropion is expected to yield similar distributions of measured and unmeasured variables of interest. This design provides a strong basis for making inferences about causal relationships between variables by controlling a priori for a wide range of patient and situational factors, thereby increasing the validity of estimates and inferential tests. In betweengroups analyses, variables that are related to outcome which differ between groups will be included as predictors in a logit model predicting group assignment, and the predicted values of this model will be incorporated as a covariate in all subsequent analyses. This includes factors that could influence treatment response [125-127], including number of prior episodes (>2 or not), treatment response vs. remission during treatment, and sex [128]. Continuously distributed outcomes will be summarized with the sample size, mean, standard deviation, median, minimum and maximum and categorical or binary outcomes with counts and percentages. Distributions will be examined to identify potentially influential observations (outliers) and suggest transforms (e.g., log) to normalize. The final report containing formatted tables and embedded graphics will be produced in Microsoft Word directly from the database using the SAS Output Delivery System. Analyses will use all subjects with usable data. All statistical testing will be two-sided with a significance level of 5%. The Holm-Bonferroni step down method will be applied as necessary to correct for multiple testing. SAS Version 9.2 for Windows (SAS Institute, Cary, North Carolina) will be used throughout.

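### The Hypothesis 2 and 3 models pool dialysis and non-dialysis patients without a dialysis term, which can distort the marker-symptom associations of Hypothesis 3 even when the arms are balanced.

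*Combined protocol and SAP*

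**What the plan says.** **Population.** Patients on hemodialysis, on peritoneal dialysis, and on neither are all eligible. The last group qualifies by "Estimated glomerular filtration rate below 59 mL/min per 1.73 m" squared. No expected mix is given.

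**Treatment.** The starting bupropion regimen is split by dialysis status. One rule reads "For patient on hemodialysis or peritoneal dialysis, oral administration of bupropion SR tablet at a dose of 150 mg on the 1st" (it goes on to name a second dosing day in the dialysis week); the other reads "For patient not on hemodialysis or peritoneal dialysis, generic bupropion SR tablet will be dosed at 150 mg daily". Fluoxetine has a single schedule: "Oral administration of fluoxetine tablet will be started at a dose of 10 mg/day", then titrated, with no split.

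**Sampling.** Under Biochemical Measurements, plasma for inflammatory markers, tryptophan (TRP) and its metabolites "will be obtained at mid-week prior to dialysis on weeks 1, 4, and 12". No timing is given for patients who are not dialysed.

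**Allocation.** It is described only as random (sections 3 and 6, General Methods); section 6 reads "Eligible CKD patients with MDD will be randomly assigned to 12 weeks of open label, flexible dose treatment". No stratum, block or minimisation factor is mentioned.

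**Models.** Testing Hypothesis 2 uses group, time and their interaction. Testing Hypothesis 3 uses time, the ratio of TRP to large neutral amino acids (TRP/LNAA) and their interaction, with neither a treatment nor a dialysis term. Exploratory Analyses add age, sex, baseline Ham-D and baseline dental disease. Dialysis status is named in none of these.

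**The only possible route in.** General Methods says that in between-group analyses "variables that are related to outcome which differ between groups will be included as predictors in a logit model predicting group assignment", with the fitted value carried as a covariate into later analyses. The factors mentioned are prior episodes, response versus remission, and sex.

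**The concern.** Dialysis status is known for every patient before the first dose, because it decides the bupropion regimen. The Background section says that hemodialysis patients have raised cytokines and markedly raised kynurenine and quinolinic acid, that free TRP can climb between sessions, and that up to 87% of patients with end-stage disease on hemodialysis show some cognitive impairment. In the protocol's own account, then, dialysis is related to the Hypothesis 3 predictors and to at least one of its outcomes. That is the structure of a confounder. A model that pools the two kinds of patient and omits the factor may read a difference between dialysis and non-dialysis patients as a link between marker and symptom, or may mask a real link if the two gaps run in opposite directions.

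For the between-arm comparison of Hypothesis 2, the stake is smaller: precision, and the effect of a chance imbalance in the one trial that is actually run.

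The plan already sets out to control dental disease and chronic pain as confounders. It does not do the same for the factor that defines its own subgroups.

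**Working it through.** **Inputs from the plan.** 20 per arm; two-sided alpha 0.05; Hypothesis 2 power 0.80 at d=0.6 with four occasions, r=0.50 and a baseline covariate; planned Hypothesis 3 correlation about 0.30 (all under Determination of Sample Size and General Methods). **Assumed, because the documents give no figure:** the dialysis share, and the gaps between dialysis and non-dialysis patients in markers and outcomes.

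**1. The plan's own figures.** Under compound symmetry the mean of four measures has variance (1 + 3×0.5)/4 = 0.625. Scaling for the baseline covariate by 1 − 0.5² gives 0.625 × 0.75 = 0.469. The standard error of the arm difference is √(0.469 × 2/20) = 0.217, so power is Φ(0.6/0.217 − 1.96) = 0.79. This matches the stated 0.80. The conversion d/√(d² + 4) = 0.6/√4.36 = 0.29 matches the stated r of roughly 0.30.

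**2. Hypothesis 3: association produced by pooling alone.** Suppose marker and outcome are unrelated within each dialysis group, with within-group SD 1, marker gap m, outcome gap g and dialysis share 0.5. The pooled correlation is

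r = 0.25·m·g / √[(1 + 0.25m²)(1 + 0.25g²)].

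Rejection probability uses Fisher's z with n=40: z = atanh(r) × √37.

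| Marker gap m (SD) | Outcome gap g (SD) | Spurious r | P(reject at 5%) |
|---|---|---|---|
| 1 | 0.3 | 0.075/√(1.25 × 1.0225) = 0.07 | 7% |
| 1 | 0.8 | 0.20/√(1.25 × 1.16) = 0.17 | 17% |
| 2 | 0.3 | 0.15/√(2 × 1.0225) = 0.10 | 10% |
| 2 | 0.8 | 0.40/√(2 × 1.16) = 0.26 | 37% |

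Arm does not appear in this calculation, so balancing the arms does not change it. This is a single-time-point approximation, not a simulation of the planned repeated-measures model.

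**3. Hypothesis 2: how often imbalance arises.** Taking the dialysis counts as two independent Binomial(20, p), the probability of a gap of 5 or more is 15% at p=0.5, 12% at p=0.3 or 0.7, and 4.5% at p=0.85.

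**4. Hypothesis 2: what a 5-patient gap does.** The difference in dialysis share is 5/20 = 0.25. Take an assumed dialysis effect of 0.5 SD.

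- If dialysis alters change itself by 0.5 SD, the shift is 0.25 × 0.5 = 0.125 SD, which is 21% of d=0.6. The conditional type I error is P(|Z + 0.125/0.217| > 1.96) = 8.9%.
- If dialysis is a stable level difference, baseline adjustment with r=0.50 leaves 0.5 × (1 − 0.5) = 0.25 SD. The shift is 0.25 × 0.25 = 0.06 SD, about 10% of d=0.6, and the conditional type I error is about 6.0%.

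**5. Would the logit rule catch it?** The plan does not define what counts as differing between groups. If it means p<0.05, Fisher's exact test gives 0.34 for 12 versus 8, 0.20 for 13 versus 8 and 0.11 for 13 versus 7. None would trigger the rule.

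**6. Effect of the covariate on Hypothesis 2 power.** If dialysis explains a gap g in the analysed outcome at a 50% share, the variance falls to 0.469 − 0.25g². Power at d=0.6 becomes 0.81, 0.85 and 0.93 for g = 0.3, 0.5 and 0.8, against 0.79 without the term. If g = 0, the t-based power goes from 0.770 to 0.769.

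**The case against.** Several points on the other side have force.

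- **The models do not strictly ignore dialysis status.** The list of factors in General Methods is not closed, so the logit rule could admit it. This stands, but the rule acts after the data are seen, has no threshold, and looks only at differences between arms. It does not reach Hypothesis 3 confounding when arms are balanced, even if its fitted value is carried into that model.
- **A reader might infer that chance imbalance biases the arm comparison, or is likely.** The documents support neither. Randomisation makes the comparison unbiased on average and leaves the unconditional type I error intact. Much of the recruitment is through dialysis centres, so a high dialysis share is plausible, and that makes large gaps rarer.
- **A reader might infer that arm imbalance is what distorts the biomarker results.** It cannot be the route, because the Hypothesis 3 model has no treatment term.
- **A reader might infer that dialysis is the strongest source of variation here.** No passage compares dialysis with non-dialysis patients. The Background attributes low total TRP to chronic kidney disease generally and names dental disease as the most common cause of inflammation.
- **Hypothesis 3 is worded in terms of change, and Hypothesis 2 analyses change, so a stable level gap could drop out.** For Hypothesis 2 this is largely right: it cancels in a pure change score and halves under baseline adjustment. For Hypothesis 3 the model as written regresses outcome measures on the ratio over time and does not restrict either to change, so level differences between patients still contribute.
- **This is a small pilot, and stratifying it is a matter of preference.** Agreed. Stratification would also do nothing for Hypothesis 3.

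**Conclusion.** The point holds in a limited form. Dialysis status affects bupropion dosing and marker sampling and is linked by the protocol to both markers and cognition, but it is absent from the Hypothesis 2 and 3 models.

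The main consequence is for Hypothesis 3. Under the assumed gaps, pooling alone could produce a correlation ranging from negligible (0.07) to close to the planned effect (0.26). With opposite signs it could conceal a real one of that size. The range depends wholly on the assumed 50% share and gaps, and on the single-time-point approximation.

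For Hypothesis 2 the consequence is modest and conditional: a shift of about 0.06 to 0.125 SD in the minority of allocations with a 5-patient gap, if the dialysis effect is 0.5 SD. The Hypothesis 1 baseline contrast is made within each arm, so arm imbalance does not bias it. The documents do not support saying that the randomised comparison is invalid or that allocation must be stratified.

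**What to change.** Prespecify baseline dialysis status (yes/no) as a fixed covariate in the Hypothesis 2 and Hypothesis 3 mixed models, whatever imbalance is observed, and state that for this factor it replaces reliance on the logit rule in General Methods.

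The cost is one degree of freedom. The factor is already known for every patient, no extra patients are needed, and the change can be made before analysis even if enrolment has ended.

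Stratifying the allocation of patients still to be randomised by this single factor is optional.

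Two matters are not resolved by the covariate. Any difference in the treatment effect between dialysis and non-dialysis patients that arises from the split bupropion regimen needs a treatment-by-dialysis interaction, which can be listed as exploratory given 20 per arm. The plan should also state when marker blood is drawn in patients who are not dialysed.

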#### Choices of bupropion and fluoxetine for the treatment:

Bupropion is unique amongst antidepressants because it selectively blocks reuptake of NE and DA without having appreciable affinity for postsynaptic receptors including histamine, α- or β-adrenergic, 5-HT, or acetylcholine [30, 88]. This confers a favorable side effect and safety profile [89], absence of weight gain [90] or somnolence [91]; side effects frequently reported by HD patients with other antidepressants [92-95]. Bupropion has no clinically significant effects on the cardiovascular system (e.g., heart rate, blood pressure, QTc interval) in patients with MDD [96]. It can increase the incidence of seizures [97] in a dose-dependent (>450 mg/day) [30] fashion in patients with a history of seizures; therefore it is contraindicated in these patients. Bupropion may preferentially reduce a subset of symptoms of MDD common in medically ill patients, including fatigue, drowsiness, cognitive dysfunction, anhedonia, and mental concentration [98, 99]. In healthy humans, after oral administration, bupropion is rapidly and ~100% absorbed by the intestine, metabolized in the liver, and excreted via kidney. The hepatic cytochrome P450 (CYP) 2B6 catalyzes bupropion to a primary active metabolite, hydroxylbupropion. Several studies [62, 100, 101] have provided guidelines and recommendations about antidepressant agents in patients with ESRD/HD. One study [80] determined the PK of bupropion and its active metabolites in HD patients following a single 150-mg oral dose and found comparable PK profile to individuals with normal renal function. Compared with controls, hydroxyl-bupropion demonstrated a >2fold greater AUC and substantially increased t1/2, indicating reduced clearance. Based on these data, the authors [80] suggested an oral dose of 150 mg bupropion every 3 days in HD patients.

While it has been suggested that antidepressants may in general reduce inflammation, research data suggests that SSRIs and tricyclic antidepressants may not. Other hand, there has been considerable recent interest in the anti-inflammatory effects of bupropion, although more research is needed [102]. Brustolim et al. [33] demonstrated that bupropion significantly reduced the levels of TNF- $\alpha$  in mice challenged with lipopolysaccharide and suggested that this effect might have important clinical consequences. In case reports, Kast and Altschuler [35, 36] proposed the potential anti-inflammatory

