#### For patients on HD

- have patent and non-infected arteriovenous fistula or graft;
- are receiving maintenance HD 2-3 times per week;

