Participation of an eligible subject in this clinical trial is a voluntary process. Subjects will not be coerced or influenced by the study personnel. In order to participate, subjects will have to voluntarily initiate a phone screening and subsequently come to a face-to-face consent/initial evaluation meeting. A research staff member or study investigator will conduct the consent process in order to minimize the possibility of undue influence from the treating physician on their hemodialysis team. Subjects will be informed that participation is voluntary and not participating will not affect the delivery of the routine health care. They and their treating physicians will be informed that the medications being used in the current study are routinely available and relatively inexpensive to obtain. They do not have to participate in this study to receive any of the treatment options.

Subjects are randomly assigned to open label treatment with one of two medications. Therefore, there are two groups:

- Bupropion group:
  - For patient not on hemodialysis, oral administration of bupropion SR tablet at a dose of 150 mg daily. Bupropion SR doses will be adjusted upward or downward based on tolerability and response.
  - For patient on hemodialysis or peritoneal dialysis, oral administration of bupropion SR tablet at a dose of 150 mg on the 1st and the 3rd dialysis day of each week. Bupropion SR doses will be adjusted upward or downward based on tolerability and response.
- Fluoxetine group: Oral administration of fluoxetine tablet will be started at a dose of 10 mg/day for the first week and then increased, as tolerated to 20 mg/day for weeks 2–4. After this, doses will be adjusted based on clinical response and side effects up to a maximum dose of 60 mg/daily by week 10.

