#### Study Intervention #1 Benefits Bupropion SR Group Bupropion SR Group Possible improvement in depression status Reasonably foreseeable risks: **Not serious** Serious Dizziness None These risks are expected to occur Agitation in more than 10 out of 100 Blurred vision subjects. Tremor Sweating Headache/migraine Inability to get adequate sleep Increased heart beat Dry mouth Constipation Decreased appetite Nausea, vomiting Weight gain **Serious Not serious** Less likely High blood pressure (Hypertension) Abnormal heart rhythm These risks are expected to occur Low blood pressure (Hypotension) in 2-9 subjects or less out of 100 Skin rash and itching subjects. Impotence Urinary frequency **Arthritis** Slowness in movement (bradykinesia) Upper respiratory complaints Fatigue Anxiety Decreased sexual desire (libido) **Serious** Rare These risks are expected to Urinary retention 1) Suicidal ideation occur in less than 1 subject in 100. 2) Suicide 3) Faint (syncope) 4) Seizures. In doses over 400mg per day, bupropion SR can be associated with seizures. The incidence of seizure with bupropion SR at the usual daily dose of 300 mg is approximately 0.1%, (or 1 out of 1000 patients), increases to approximately 0.4% at the maximum dose of 400 mg/day. The dose of 150 mg twice per week used in this study was previously shown to lead to blood levels in hemodialysis patients comparable to those obtained during routine treatment of non-hemodialysis patients treated with 300 mg daily.

Version #: 17, IRB #203076

PI: [name]

Study Intervention #2 Benefits							
Fluoxetine Group							
Fluoxetine group	Possible im	provement in depression status					
Reasonably foreseeable risks :							
	Not serious		Serious				
Likely These risks are expected to occur in more than 10 out of 100 subjects.	

Decreased app

Anxiety

Nervousness

Inability to obtasleep (insomni

	ain adequate	• None				
	Not serious		Serious				
Less likely These risks are expected to occur in 2-9 subjects or less out of 100 subjects.	• Impaired	thinking	

Alteration in blood glucose

Abnormal bleeding

Weight loss

				
			Serious				

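### The bupropion starting rule for dialysis patients does not work for eligible patients on twice-weekly hemodialysis; followed literally it yields half the stated study dose (minor)

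*Combined protocol and SAP*

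**What the plan says.** Under the Study population heading, the criteria for hemodialysis patients require that they "are receiving maintenance HD 2-3 times per week". Both two and three sessions a week are therefore eligible.

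The bupropion starting schedule for dialysis patients appears three times, with the same content each time: in the list of treatment groups in section 5 (Consent Process), in the same list in section 6 (Research Plan), and in the procedures text of section 6. The list in section 6 reads "oral administration of bupropion SR tablet at a dose of 150 mg on the 1st and the 3rd dialysis day of each week". The procedures text reads "generic bupropion SR will be dosed at 150 mg on the 1st and the 3rd dialysis day of each week", and participants are "instructed to begin the medication on day 1 (1st dialysis day) of week 1 of the study". None of the three places gives a schedule for a week with two sessions. The treatment lists then allow the dose to move up or down with tolerability and response, without numeric steps.

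The risk table for the bupropion group states the weekly frequency directly: "The dose of 150 mg twice per week used in this study was previously shown to lead to blood levels in hemodialysis patients comparable". The comparison is with patients off hemodialysis who take 300 mg daily.

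**The concern.** The rule picks out dialysis days by ordinal number, and the second of the two ordinals exists only in a three-session week. The words *of each week* also rule out carrying the count over into the following week. For a patient dialysed twice a week, the only day that meets the rule is the first.

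That result conflicts with the risk table, which gives twice-weekly dosing as the study dose and does not limit it to patients with three sessions. The table's statement about blood levels attaches to two doses a week. The documents say nothing comparable for one dose a week.

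The practical stake is the starting instruction for an expressly eligible group. The research pharmacy labels each supply with directions for use, so someone has to decide what a twice-weekly patient's label says. One person could apply the rule as worded and another could apply the risk table, and two similar patients would then start on different doses. Later adjustment does not settle this. Fluoxetine has defined steps (10 mg, then 20 mg, up to 60 mg by week 10), but bupropion has no numeric titration schedule that would bring a low start back to the intended level.

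**Working it through.** **Inputs**

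- Dose per administration: 150 mg (sections 5 and 6).
- Dosing days: sessions number 1 and number 3 within each week (sections 5 and 6).
- Eligible sessions per week, *s*: 2 or 3 (section 4, criteria for patients on HD).
- Stated study dose in hemodialysis patients: 150 mg twice per week (risk table, bupropion group).

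**Formula**

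Doses per week = how many of sessions 1 and 3 exist in a week with *s* sessions. Weekly dose = 150 mg × doses per week.

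**Reproducing the plan's own figure**

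Risk table: 2 × 150 = 300 mg per week. With *s* = 3, sessions 1 and 3 both exist, so there are 2 doses and 2 × 150 = 300 mg per week. Ratio to the stated dose: 300/300 = 1.0. The rule and the risk table agree.

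**The other eligible case**

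With *s* = 2, session 1 exists and session 3 does not, so there is 1 dose and 1 × 150 = 150 mg per week. Ratio: 150/300 = 0.50.

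| Sessions per week | Doses under the rule | mg per week | Ratio to 300 mg | Mean interval |
|---|---|---|---|---|
| 3 | 2 | 300 | 1.0 | 7/2 = 3.5 days |
| 2 | 1 | 150 | 0.50 | 7/1 = 7 days |

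**After the proposed change**

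With the dosing days defined as the first and last hemodialysis day of the week, *s* = 3 gives sessions 1 and 3, and *s* = 2 gives sessions 1 and 2. Both give 2 × 150 = 300 mg per week, in agreement with the risk table.

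**How many patients**

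The documents do not say how many participants are expected to be on twice-weekly hemodialysis. The number affected lies between none and every hemodialysis patient in the bupropion arm, which is planned at 20. No sample size, power or alpha figure uses this schedule as an input.

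**The case against.** The strongest reply is that the rule is incomplete rather than wrong. It does not order one tablet a week; it names a day that some patients do not have. The protocol also uses the term loosely. The instruction to start on the first dialysis day is addressed to all participants, although patients not on dialysis are eligible too. A strictly literal reading is therefore weak evidence that anyone would actually receive half the dose. The risk table makes the intent plain. Study physicians see patients at weeks 1 to 4, dosing is open label and flexible, and hydroxybupropion is measured at week 4.

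Much of this stands. It limits the point to a minor one. It does not remove it, because the only three statements of the schedule share the same gap, and filling it literally contradicts the protocol's own figure.

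A reader might infer four stronger things that the documents do not support.

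- *That twice-weekly patients will be underdosed.* The text shows only what the rule yields if followed literally. Staff can read the risk table, and the dose may be adjusted after the start.
- *That the right yardstick is the cited pharmacokinetic study.* Its authors, as the Background reports, "suggested an oral dose of 150 mg bupropion every 3 days in HD patients", which averages 150 × 7/3 = 350 mg per week. Against that, one dose a week is 150/350 = 43%. But the protocol says only "The initial dose of bupropion-SR is based on the findings of" that study and does not adopt its interval. Even the stated twice-weekly dose is 300/350 = 86% of it. The relevant comparison is 150 with 300 mg per week.
- *That power, adherence analysis, 12-week exposure or the comparison between arms is compromised.* The number of such patients is unknown, doses are flexible, and the literal error runs toward a lower dose. Nothing here permits such a claim.
- *That peritoneal dialysis patients could be given the daily dose.* Section 5 says "For patient not on hemodialysis, oral administration of bupropion SR tablet at a dose of 150 mg daily", without mentioning peritoneal dialysis. The next bullet there, and section 6, place those patients under the dialysis schedule. That wording is clerical and not part of this point.

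**Conclusion.** The point holds as a minor error of wording. The starting rule does not work for hemodialysis patients with two sessions a week, a group that the eligibility criteria expressly admit. Read literally, it gives 150 mg a week against the 300 mg a week in the risk table, a ratio of 0.50. For three sessions the two places agree.

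The conclusion rests on two readings: that dialysis days are counted afresh within each week, as the rule says, and that the risk table's twice-weekly dose applies to all hemodialysis patients, since it names no exception. It concerns the starting schedule only. It is worth correcting because it is a dosing instruction, it is repeated in every place where the schedule is given, and the remedy is one line.

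**What to change.** In section 5 (Consent Process) and at both places in section 6 (Research Plan), replace the reference to the first and third dialysis day with: *150 mg twice per week, on the first and last hemodialysis day of each week (the 1st and 3rd sessions if dialysed three times weekly, both sessions if dialysed twice weekly)*. The study physicians should confirm that two doses a week is the intended start for twice-weekly patients.

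If the same sentence continues to cover peritoneal dialysis, add that those patients take the two doses on non-consecutive days about 3 to 4 days apart. Asking only for two fixed days would not be enough, because it would allow doses on consecutive days.

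The cost is a wording edit in three places. Three-session patients keep their present schedule, the risk table needs no change, and sample size, visits, assessments and analysis are unaffected.
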